5.3.2 Additional Screening Procedures and Considerations

Participants will also have to meet the additional inclusion/exclusion criteria (such as, but not limited to, stability on medications per appendix H). As well, in regards to hematologic values from screening visit labs, if screening ANC>70% or 7.7X10³/mm3 or WBC>11,500/mm³ and if this is sustained for > two weeks on recheck, a medical evaluation and clearance for underlying conditions, as well as return to normal prior limits, must be met prior to consideration for further enrollment procedures.)

To determine whether inclusion/exclusion criteria are met, a review committee consisting of the principal investigator or delegated sub-Investigator and the trial coordinator will review all screening data points. If all inclusion/exclusion criteria are met, with results reviewed by the principal investigator or qualified sub-investigator, the principal investigator or delegated sub-investigator will provide documented confirmation that the participant is eligible to be randomized. After that confirmation, the participant may complete their optional Tier 4 Screening Visit or Baseline Visit. More detailed information of this process can be found in a separate document, the Manual of Procedures.

5.4 Double Blind Treatment Period (Baseline Visit through Visit 24)

The treatment period is double-blinded, beginning at the Baseline Visit. At the Baseline Visit, appointments for all remaining visits should be made and scheduled as close as possible to the targeted date, based on the Baseline Visit. Visits done outside the allowable window will be considered a protocol deviation. Participants who meet the entry criteria for the clinical trial will be enrolled, randomized, and receive 24 weeks of treatment with either sargramostim or placebo.

The participant will follow the schedule of 7 days (Sunday through Saturday) of subcutaneous injection (178.57 µg/m²/day sargramostim or placebo) over the course of 24 weeks, for a total maximum of 168

treatment days. The first injection will be administered at the time of baseline (randomization) visit in the site's designated facility. The participant and study partner will receive training and a schedule on how to administer additional doses at home. For the first 3 weeks, the participant will receive a weekly dose administered by their caregiver with observation by a study nurse for correct injection technique. After the first 3 weeks, the injection will be observed by a study nurse at in-person visits at the site (Wk 6, Wk 12, Wk 18). Ongoing injection technique education will be provided as needed. If the caregiver is unable to administer the in-person visit injection, the injection will instead be administered by a trained medical professional. The investigational product will be distributed weekly to the participant either at their inperson clinic visit (Baseline, week 6, week 12, week 18) or at-home visit for subsequent subcutaneous injection at home, along with a new injection diary. An empty sharps container will be provided at the baseline visit and be replaced as needed for participants/caregivers to place used syringes into at home.

At the weekly double-blind treatment period site visits (Visit 2- through Visit 24), delegated study personnel will review and record changes to conmeds, adverse events, compliance and vital signs. As well, qualified staff will review inject sites to assess for possible adverse reactions.

5.4.1 Double-Blind Treatment Procedures

All treatment visit administrative procedures, cognitive assessment, safety assessments and laboratory assessments are to be done before administration of the investigational product.

5.4.1.1 Baseline Visit Procedures

- Randomization
- Concomitant medication and AE review
- Physical/neurological exam
- Vital sign / weight
- Cognitive assessments and other measures

Participant

- o Mini-Mental State Examination (MMSE)
- o Alzheimer's Disease Assessment Scale cognitive subscales (ADAS-Cog₁₃)
- o Trail Making Test-A (TMT-A)
- Verbal Fluency (Lexical and Semantic Fluency)
- o MoCA
- o Clinical Dementia Rating Scale (CDR)
- o GDS
- o GAD-7
- o C-SSRS

Study Partner

- o CDR
- o Alzheimer's Disease Cooperative Study Activities of Daily Living Inventory (ADCS-ADL)
- Neuropsychiatric Inventory (NPI)
- Sleep assessments (ISI, PSIQ)
- Laboratory assessments
- FDG PET
- IP administration training
- Administration of first dose
- Dispensing of IP

Note: It is acceptable to perform the required procedures of the baseline visit over more than one visit to accommodate the participants and study site scheduling.

At the Baseline Visit, the pharmacy will be contacted to perform participant randomization (this may be

done in advance of the visit to allow for study drug / placebo preparation by the pharmacy), a physical exam is performed, vital signs are recorded, approximately 52 ml of blood will be drawn for a CBC with differential, a CMP, ADA evaluation (anti-sargramostim antibodies), and for biomarker assays (e.g. NfL, UCHL1, GFAP, IL-6, BDNF, etc.). As well, a sample will be obtained and stored for later ApoE genotyping.

Baseline assessments of cognition will be conducted by trained personnel, including the, MMSE, MoCA, ADAS-cog₁₃, ADCS-ADL, Trail Making Test-A, CDR, NPI, and the verbal fluency measures (lexical and semantic). (Note that the qualified clinical rater who administers the CDR and ADCS-ADL will not be the same individual who administers the remainder of the cognitive assessment, thereby ensuring that CDR raters are blind to other clinical data.) Additionally, safety assessments, (i.e. C-SSRS, GDS and GAD-7) will be administered. More information about these testing assessment procedures can be found in a separate document, the Manual of Assessments.

The investigational product will be prepared by the unblinded pharmacist for acceptance by study personnel, with the initial dose administered by the study partner or designated caregiver after injection technique education by a study nurse with study nurse oversight, or by a study nurse if needed. Investigational product administration training will be given, with injection diary, to the participant and study partner. The remaining injections will be administered by or under the supervision of the study partner or other designated caregivers in the home setting until the next in-person visit. More detailed information can be found in a separate document, the Manual of Procedures.

5.4.2 Additional Double Blind Treatment Study Procedures

In addition to the regularly scheduled collection of vital signs, conmed and AE review, labs, cognitive assessments, imaging and a physical/neurological exam will be completed at visits 12 and EOT. More detailed information can be found in a separate document, the Manual of Procedures.

Pharmacy orders will be submitted using the most recent weight documented for each participant, and coordinators will ensure the weight is within 3-weeks of the order submission. If a new weight is documented after order submission and by noon the day before the pharmacy dispenses, the coordinator will verify if the weight has changed by more than 3%. If the change is greater than this amount, a new pharmacy order will be submitted with the updated weight. If the change is less than this amount, the order will proceed with the original submission.

5.4.2.1 Double-Blind Treatment Labs – Visit 2 through 24

Prior to investigational product administration at weekly visits (Visit 2 through Visit 24), either at-home visits or research site visits, qualified medical staff will draw blood for safety labs and metabolic functioning (approximately 8 ml for CBC with differential and CMP) with two CBC with differential and one CMP per study week. Additionally, prior to administration of investigational product, on specific visits (Visit 6, 12, 18 and 24), there will be an additional blood draw for ADA testing (approximately 9 ml). If there are outstanding clinically significant lab values after CMP during week 24, additional CMP lab draw(s) may take place to resolve these clinically significant values, or the participant referred to their health care provider for clinical care follow-up, based upon the judgement of the PI.

An additional, weekly, safety blood draw (i.e. CBC with differential) will be completed. Depending on the participant's preference, the participant can either visit the CU -AMC site for the blood draw or the participant can travel to a local contracted lab site and have the safety draw (i.e. central contracted laboratory with phlebotomy services, as specified in Manual of Procedures). Lab results will be forwarded to study staff for review by the study physician. The EOT and FU Visits will comprise of a safety blood draw CBC w/differential and other specified labs per the schedule of events).

Additionally, a PT INR will also be drawn at Visit 24 in preparation for review prior to the EOT.

5.4.2.2 Double-Blind Treatment Cognitive Assessment – Visits 12 and End of Treatment (EOT)

At Visit 12 and EOT Visit, Cognitive assessments will be conducted by trained personnel, including the MMSE, MoCA, ADAS-cog₁₃, ADCS-ADL, Trail Making Test-A, CDR, NPI, verbal fluency measures (lexical and semantic), , and sleep-related measures (i.e. ISI and PSQI). As mentioned above, there will be blinding between the cognitive and the clinical rater. As well, all attempts are to be made to schedule the assessments at approximately the same time of day, with the same rater to reduce variability.

Additionally, safety C-SSRS, GDS and GAD-7 assessments will be administered by qualified personnel at Visit 12 and EOT Visit.

5.4.2.3 Double-Blind Treatment Imaging

High-resolution MRI scans will be completed at Visit 6, Visit 12, Visit 18 and EOT Visit.

In addition to the baseline FDG PET Scan, an End of Treatment FDG PET Scan will be completed at EOT Visit.

5.4.2.4 EOT / Double-Blind Treatment blood draw and Lumbar Puncture (if applicable)

Occurring within 10 days, and at least 2 days following the final treatment day of week 24, a lumbar puncture will be conducted. Vital signs and weight will be collected at lumbar puncture visits. CSF for assays including $A\beta(1-42)$ and tau: $A\beta(1-42)$ ratios, total cell count, and for biomarker assays (e.g. NfL, UCHL1, GFAP, IL-6, BDNF, etc.) will be collected. At the same visit as the LP procedure has obtained CSF, a blood draw of approximately 44 ml will be obtained for biomarkers assays (e.g. NfL, UCHL1, GFAP, IL-6, BDNF, etc.). Additionally, both blood and CSF samples will be analyzed by UC Health to determine a serum/CSF albumin index.

5.5 Follow-up Visit

After the 24-week double-blind treatment period, all participants will be monitored during a 45-day follow-up period. At this visit, a physical/neurological exam will be performed, vital signs recorded, draw approximately 52 ml of blood for a CBC with differential, ADA analysis, and biomarker assays, and administer cognitive tests, including the MoCA, MMSE, ADAS-cog₁₃, the ADCS-ADL scale, Trail Making Test A, CDR, NPI, verbal fluency measures (lexical and semantic), and sleep-related measures (i.e. ISI, PSQI).

If the participant opted to engage in the Amyloid PET scan (either as entry criteria or optional), the PET will be performed using Vizamyl, and an MRI will be performed.

5.6 End of Treatment / End of Study Definitions

End of Treatment is the date of the last Visit or scheduled procedure for a participant, as listed in the Schedule of Events (Section 2)

End of Study is the date of the last Visit or scheduled procedure for the last participant randomized, as listed in the Schedule of Events (Section 2)

Every attempt should be made to follow participants through their final visit of the double-blind treatment phase and follow-up visit. If a participant discontinues the study prematurely for any reason, all reasonable attempts will be made to complete an Early Termination Visit, which will consist of the events listed for the End of Treatment Visit.

5.7 At-Home Visits

As noted above, when the option becomes available to participants, nurses, contracted through an accredited traveling or in-home nursing organization, will be utilized to provide at-home visits during the treatment period of the clinical trial. The nurse(s) will visit the participant's home one day per week (Monday through Friday, as their selected day as designated by study staff) during weeks 2–24 (excepting weeks with inclinic visits, week 6, week 12, and week 18, as described above) to verify delivery/presence of the weekly doses of the study drug, record vital signs, perform injection sites review, record conmed changes, record adverse events, and draw blood. Participants will also be given the option to come to the study site for their weekly visits, rather than have home visits. Except under extenuating circumstances, participants will be discouraged from switching the location of the weekly visits.

5.7.1 Narrative Summary of Home Visits:

Each participant's first injection will be administered at the time of baseline (randomization) visit in the Clinical and Translational Research Center (CTRC) at the CU-AMC campus. As noted above, injections for the first 3 weeks, at in-person visits either at home, or in-clinic (select visits) will be administered by the study partner under observation by a trained (blinded) study nurse after training by study staff, and under observation at Wk 6, Wk 12, and Wk 18 on site study visits, with refresher training as necessary. At the Home visits (weeks 2-5, 7-11, 13-17, 19-24), the nurse will verify delivery of the study drug (by a contracted delivery service), collect vital signs, perform an injection site review, and record adverse events. As well, the nurse will perform a blood draw of approximately 4 mL for CBC plus differential on the day of each home visit for safety labs, and deliver to the contracted central laboratory.

5.7.2 Summary of Traveling Nurse Duties During at Home Visits:

- Verification of delivery study drug to home of participant
- Perform and record vital signs
- Injection sites review
- Record and monitor Adverse Events.
- Record conmed changes, if any
- Blood draw (CBC + Diff,) at each home visit;,; deliver blood samples to contracted laboratory drop-off site within two hours of collection.
- Oversee administration, by study partner, of study drug injection until Week 3 and as needed thereafter.
- Provide injection training refresher, as necessary.
- Return injection diary and all other study visit related paperwork to study staff.

5.7.3 Logistics Associated with Traveling Nurses:

Day before/day of visit: The study drug will be collected from the CU Outpatient Research Pharmacy by for delivery to the participants residence. The study drug syringes will be placed in hard cases, in an insulated bag with a cold pack for transport. Refrigeration required for drug: drug to be placed in the refrigerator at the participant's residence, with a recording thermometer (supplied by the study).

Day of Visit: Nurse will travel to participant's residence to perform the required duties (verify delivery of drug, injection site review, check vital signs, monitor adverse events, oversee injection of study drug by study partner as needed, draw blood, complete source documentation, injection site diary, drop off blood samples to lab). Submit data updates daily/ every-other-day (unless urgent) to study team.

At Home Visit Nurse requirements:

- Current nursing license with the State of Colorado (LPN or higher)
- Current driver's license with no outstanding citations.
- Reliable vehicle
- Coordinated back up from employer

5.7.4 Drug Handling Details (when performed by courier service for at home visits):

Study drug will be provided with a temperature monitoring device, which will record the temperature and record an excursion if the temperature is outside of the established range for the study drug when stored in the participant's home refrigerator. On the designated day for the home visit (or day before if able to be appropriately stored), the study drug will be picked up by an authorized staff member at CUAMC Research Pharmacy, and either deliver it to the participant's home, or delivery will pick up from AMC staff and deliver it to the participants home, and the study partner will placed in the refrigerator. During transit from CUAMC to the participant's home, the pre-filled syringes will be maintained in a temperature-controlled container in a hard case designed to prevent any inadvertent changes to the syringes. As well, a temperature-monitoring device will be placed in the container with the drug to ensure proper temperature exposure and provide a read-out of temperature reading if an excursion is noted. The temperature-monitoring device will be left in the participant refrigerator with the study drug and reviewed at in-person visits by the study team.

6 Study Population

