5.1 Overall Design

The study is a Phase 2, double-blind, placebo-controlled study of sargramostim in the Alzheimer's disease population. It will include individuals diagnosed with mild AD or moderate AD (or meeting criteria consistent with a provisional research diagnosis), consistent with MoCA score range of 4-24 (137, 138,139) at time of screening and NIA-AA (2018) research criteria. The study includes a screening period of up to 12-weeks, a treatment period of 24-weeks, and an approximately 6-week follow-up. Individuals who meet inclusion/exclusion criteria will be randomized in a double-blind manner, in an approximate 2:1 randomization ratio to one of the following treatments:

- Sargramostim 178.57 μg/m²/day subcutaneously (7 days per week) (This is adjustment from original 250 μg/m²/day subcutaneously (5 days per week). Any participant on the original dosing schedule will be changed to the new dosing schedule the first refill after amendment is approved)
- Placebo equivalent volume subcutaneously (7 days per week).

The estimated maximum main study visits for each individual participant is approximately 55, including 4 screening visits (Tier .5-3), 48 treatment period visits (i.e. 4 in-person clinic visits, 20 at home visits, and 24 weekly blood draw at central laboratory for 2nd safety CBC w/diff), 1 End of Treatment visit, 1 FDG PET visit, and 1 visit in the post-treatment follow-up phase. Participants who opt to participate in the optional PET substudy or optional LP substudy would have 2 additional visits, 1 during screening, and 1 during either EOT (LP) or follow-up (PET). All participants will have the option of visits to happen at the main study site when the home nursing visit option is available.

5.1.1 Investigational Product:

Recombinant human GM-CSF is commercially available from Partner Therapeutics as Leukine[®]/sargramostim, which is FDA-approved for use in elderly patients (> 55 years old) and has a long and well documented safety record. The investigational product will be obtained by the study Sponsor for use in this clinical trial, and prepared by an unblinded pharmacist for administration to the randomized participant.

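### Section 5.7 gives the home nurse a CBC-only draw and no weight, contradicting the weekly CMP and weight that Section 5.4.2.1 and the Schedule of Events require at the same visits

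*Protocol*

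**What the plan says.** **Visit pattern.** Section 5.1 plans the treatment period as "4 in-person clinic visits, 20 at home visits, and 24 weekly blood draw at central laboratory for 2nd safety CBC w/diff". Section 5.7.1 places the home visits by week: "At the Home visits (weeks 2-5, 7-11, 13-17, 19-24), the nurse will verify delivery of the study drug". Home visits depend on the service being available, and participants may attend the site instead (Sections 5.1 and 5.7).

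**Home-visit duties.** Section 5.7.1 states that "the nurse will perform a blood draw of approximately 4 mL for CBC plus differential on the day of each home visit". The duty list in Section 5.7.2 has "Blood draw (CBC + Diff,) at each home visit". Neither mentions a CMP, a weight or PT/INR. The introduction to 5.7 and Section 5.7.3 speak only of drawing blood, without naming tests.

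**Requirements elsewhere for the same visits.**
- Section 5.4.2.1 applies "at weekly visits (Visit 2 through Visit 24), either at-home visits or research site visits" and says that "qualified medical staff will draw blood for safety labs and metabolic functioning (approximately 8 ml for CBC with differential and CMP", with one CMP and two CBCs per study week. The synopsis and Schedule footnote k also set the CMP at once a week.
- The second weekly draw is a CBC with differential only (Sections 5.1 and 5.4.2.1).
- The Schedule marks Weight at every visit, and Section 8.4.3 refers to it for body weight.
- For pharmacy orders, Section 5.4.2 says "coordinators will ensure the weight is within 3-weeks of the order submission".
- PT/INR is scheduled at Week 24 (Schedule and Section 5.4.2.1).

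**The concern.** Two sections instruct staff differently for the same visits. The halved volume, 4 mL against 8 mL, makes it hard to read Section 5.7.1 as shorthand for the fuller draw.

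The weight cannot be assumed to fall under the nurse's vital signs. Schedule footnote j lists temperature, respirations, blood pressure and pulse, and Section 8.4.3 treats weight separately.

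Three things are at stake if a home nurse works from Section 5.7 alone:
- **Safety data.** CMP is named in the primary endpoint (Section 4.5). Kidney and liver elevations are on the list to be monitored (Section 8.4.5.3), and the interruption and discontinuation provisions in Sections 7.5 and 8.4.5.3 rely on measured laboratory values. Unmeasured weeks would also thin the safety comparison between arms.
- **Dose calculation.** Dose is set per square metre, and the protocol's own control on that calculation is the 3-week limit on the age of the weight.
- **End-of-treatment procedures.** The lumbar puncture at EOT, for those who have it, needs a PT/INR from the preceding 3 months (Schedule, footnote to the EOT procedures).

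**Working it through.** **1. Reproduce the visit count.** Weeks 2–5, 7–11, 13–17 and 19–24 give 4 + 5 + 5 + 6 = 20 home visits. Baseline and weeks 6, 12 and 18 give 4 clinic visits. 20 + 4 = 24, which matches Section 5.1.

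**2. Set the instructions side by side for a home week.**

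| Item | Schedule, 5.4.2.1, synopsis | 5.7.1 and 5.7.2 |
|---|---|---|
| Nurse's draw | about 8 mL, CBC + CMP | about 4 mL, CBC only |
| Second weekly draw | CBC only | not addressed |
| Weight | every visit | not listed |
| PT/INR at Week 24 | required | not listed |

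**3. CMP if Section 5.7 alone is followed.** Assume a participant takes every home visit. CMP is then drawn at 24 − 20 = 4 of 24 weeks, and 20/24 = 83% are missing. The last is at Week 18. Footnote k gives no CMP at EOT or follow-up, so no scheduled CMP follows, although Section 5.4.2.1 relies on a Week 24 CMP to decide whether outstanding values need repeat draws.

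**4. Age of the dosing weight under the same assumption.** Weights come only from Baseline (taken as week 1) and weeks 6, 12 and 18. Age = order week − latest clinic week, in nominal weeks. Ages above 3 are:

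| Order week | 5 | 10 | 11 | 16 | 17 | 22 | 23 | 24 |
|---|---|---|---|---|---|---|---|---|
| Age (weeks) | 4 | 4 | 5 | 4 | 5 | 4 | 5 | 6 |

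That is 8 orders. If the clinic-week orders are placed before that visit's weight is taken, week 6 (6 − 1 = 5), week 12 (12 − 6 = 6) and week 18 (18 − 12 = 6) are added: 8 + 3 = 11. The maximum age is 6 weeks in both cases.

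**5. PT/INR.** The scheduled measurements are at screening and Week 24. If Week 24 is missed, the latest result predates 24 weeks of treatment (24 × 7 = 168 days), which is beyond 3 months.

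**6. If the Schedule and Section 5.4.2.1 are followed.** CMP is taken at 24 of 24 weeks. A weight nominally 7 days old is available for each order, or at most 7 + 3 + 3 = 13 days with the ±3-day windows. That is inside the 21-day limit.

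**The case against.** The strongest reply is that the protocol already orders everything needed. Section 5.4.2.1 names at-home visits and requires the CMP, and the Schedule and Section 8.4.3 require the weight. Section 8.2 allows a contracted nurse to do the phlebotomy. Section 5.7.1 and 5.7.2 are headed as summaries, Section 8 points to the Schedule and Section 5 for procedures and timing, and detail is deferred to a Manual of Procedures that is not at hand. The weight is an omission from a list; nothing in Section 5.7 says it is not taken. Section 5.4.2 also makes coordinators responsible for the age of the weight when the order is submitted.

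Most of this stands. A reader might infer that the weekly CMP and the 3-week limit cannot be met under the protocol. The documents do not support that: both are ordered and, as step 6 shows, both are met if the Schedule is followed. Nor can one infer an 83% loss of CMPs across the trial. That figure needs a participant to use every home visit and the nurse to follow Section 5.7 over Section 5.4.2.1. The primary endpoint names CMPs but sets no frequency; the weekly interval comes from the synopsis, the Schedule and Section 5.4.2.1.

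The reply does not remove the 4 mL CBC-only instruction, which directly contradicts the 8 mL CBC-plus-CMP instruction for the same visits. A correct manual would reduce the practical risk but leave the protocol inconsistent.

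**Conclusion.** There is an internal contradiction over the home-visit blood draw, together with two omissions from the nurse's duties: the weight and the Week 24 PT/INR. It is a wording fault with possible consequences for safety monitoring and weight-based dosing.

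The figures of 4 of 24 CMPs and 8 to 11 orders on an over-age weight are upper limits for one participant. They assume all 20 home visits are taken, Section 5.7 alone is followed, no extra weight or CMP is obtained elsewhere, and visits fall on nominal weeks. Home visits are optional, so the actual share will be lower by an amount the documents do not allow one to estimate. Section 5.7 does discourage switching location, so a participant who chooses home visits could come close to the limit.

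A related inconsistency should not be folded into this one. Section 5.4.2.1 places an ADA draw at Visit 24, whereas the Schedule and Section 8.3.1 place the corresponding draw at EOT. A reader might take the Week 24 ADA draw as a Schedule item that the nurse list omits; the Schedule does not assign it there.

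**What to change.** Reconcile Sections 5.7.1 and 5.7.2 with Sections 5.4.2 and 5.4.2.1 and the Schedule of Events. The home-visit duty list and draw volume should carry the CMP, the weight and the Week 24 PT/INR, or the protocol should state where else each is taken. Check that the Manual of Procedures and any instructions given to the nursing contractor say the same.

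Separately, reconcile the ADA draw at the end of treatment between Section 5.4.2.1 (Visit 24) and the Schedule and Section 8.3.1 (EOT).

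The cost is wording, a weight measurement at a visit already taking place and, for the weekly CMP, about 8 − 4 = 4 mL more blood at an existing draw. No analysis or sample size changes.
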